Randomization			X									
 It is preferable for screening and randomization to occur on the same day. If screening occurs over 2 consecutive days, randomization must occur on the second day. Randomization and treatment start on the same day. At randomization, the participant enrolment number is assigned.
Medical History and Physical Examination												
Medical History		X										
Physical examination		X	X								X	
 Physical examination at days 3, 5, 10, 15, 28, 35, and the unplanned visit to be performed at discretion of the investigator. Physical examinations to be completed before administration of study intervention. A general physical examination is to be performed at screening/baseline on all participants, thereafter symptoms' driven. If screening and randomization happen on the same day, examination performed only once. See Section 8.3.1 for additional information.

Table 1. Study Schedule of Activities

Visit Identifier Abbreviations may be found in Appendix 11 . X = required	Pre- screen (Optional)	Screen	Treatment Period			F/U					Early Discont.	Notes
			Day 1	Day 3	Day 5	Day 10	Day 15	Day 28	Day 35	Unplanned Visit for Post- Treatment ARI (in-person)		
Visit Window	Day -4 to 1	Day -1 to 1	(0)	(±1)	(+1)	(± 1)	(± 2)	(± 2)	(± 2)	Day 6 to 28		
 See Section 8.4.3 for follow-up AE and SAE assessments.
Record signs and symptoms to confirm LRTI status		X	X	X	X	X	X	X		X	X	
 If screening and randomization happen on the same day, LRTI status is assessed only once on Day 1.
Assess clinical response					X	X	X	X				
 See Section 8.2.3.
Weight, height		X										
 See Section 8.3.1 for additional information.
Vital signs		X	X	X	X	X	X	X		X	X	
 If screening and randomization happen on the same day, vital signs are collected only once. Vital signs at day 35 visit to be performed at discretion of the investigator. See Section 8.3.2 for additional information.
12-Lead ECG		X										
 ECG to be performed after screening only as needed per investigator discretion. See Section 8.3.3 for additional information.
Contraception check		X	X	X	X	X	X	X	X	X	X	

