6.5. Study Intervention Compliance

When participants self-administer study intervention(s) at home, compliance with study intervention will be assessed at each visit as indicated in the [SoA](#).

Participants will be issued a paper dosing log and will be trained how to record the date and time of study intervention dosing on Day 1. The participant will bring the paper dosing log to each study visit until the dosing log is collected after dosing is complete.

Site personnel will review the dosing log at site visits as indicated in the [SoA](#). If any noncompliance with dosing entries is suspected or observed in the data, site personnel remind the participant of the relevant study procedures and/or entering the dosing information in the dosing log, as applicable.

Study intervention compliance and dose administration dates and times will be recorded in the CRF and will be assessed by delegated study personnel at study visits through counting returned tablets, reviewing the dosing log, and discussion with the participant, if applicable. A record of the number of tablets dispensed to and taken by each participant must be maintained and reconciled with study intervention and compliance records as source documentation. Deviation(s) from the prescribed dosage regimen should be recorded in source documents.

The following noncompliance cases will be considered medication errors and reported as protocol deviations (see Section [8.4.9](#)):

- Participants missing study intervention for 2 consecutive doses.
- Participants who have an overall study intervention compliance <80% or >120%.

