#### 3.5. Baseline Variables

Baseline risk factors include:

- age ≥ 65 years
- chronic lung disease
- heart failure
- immunosuppressed (includes immunosuppressive disease or condition, or use of at least 1 specific immune-weakening medication; this is indicated on the Pre-Specified

Significant Medical History – Risk Factors CRF with a response of 'YES' for the 'IMMUNOCOMPROMISED' term).

For laboratory assessments, vital signs, and LRTI assessments, the baseline window will be Day -2 to Day 1, without any consideration to exact time of assessment.

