#### 6.6. Baseline and Other Summaries and Analyses

#### 6.6.1. Baseline Summaries

Baseline demographic and other characteristics will be tabulated for the FAS and summarized by treatment group. This will include age, sex, race, ethnicity, weight, height, BMI, geographic region, presence/absence of specific risk factors, and number of risk factors.

The levels of geographic region will be as follows:

All baseline disease characteristics will be summarized by treatment group for the FAS. This will include symptom duration, number of days since diagnosis (start date of study treatment – date of diagnosis + 1 [if participant is randomized but not treated, randomization date will be used in place of start date of study treatment]), presence/absence of individual signs/symptoms (from the Signs and Symptoms of ARI CRF), and LRTI status (from the LRTI Assessment Details CRF; any LRTI [yes/no]; if yes, intensity grading

[mild/moderate/severe]; meet criteria for Severe LRTI? [yes/no]; RSV-related? [yes/no/unknown]).

Symptom duration is calculated as [6]

For viral load data, baseline visit is set up according to study days of Day -2 to Day 1. Only post-dose results that are within 1 hour post start of dosing will be treated as Baseline data.

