#### Appendix 2. Data Derivation Details

## Appendix 2.1. Definition and Use of Visit Windows in Reporting

The following table defines the visit windows and labels to be used for reporting other than endpoints assessed for an event through Day 28 (those endpoints use a window of Day 1 to Day 28) and PK endpoints (those endpoints use nominal visit):

- Labs, Viral load, Vital Signs, and LRTI: Baseline window will be Day -2 to 1 without any consideration to the time factor. The only
  exception to time is viral load, where baseline is within 1 hour post start of dosing. If both screening and Day 1 visits are
  collected on the same calendar day, Day 1 will be used.
- If multiple readings fall into the same window on different days, choose the one closer to the target day. If equidistant, then select
  the later one after the target day. If multiple readings fall into the same window on the same day at study start, pick Day 1 as the
  nominal visit over screening for baseline. For vital signs, average the readings if they are on the same day within 10 minutes.
- For labs and viral load, if multiple observations without time or at the same time fall on the same day after the windowing logic has been applied, average observations. If different times on the same day, select the later one.
- When data from study Day 4 has an overlap between Day 3 and Day 5 windows, decision made is to assign the window
  according to the nominal visit. The rule will not be applicable to other study days 2 and 3 for Day 3 window, and days 5 and 6 for
  Day 5 window.
- If unplanned viral load (or other outcomes) are assessed on Day 4, then it will be assigned to Day 3. If the nominal Day 3 exists
  and an unplanned Day 4 assessment is obtained, then the nominal Day 3 visit will still be chosen as the record for the Day 3
  window.

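### The SAP's baseline for labs and vital signs (and, narrowly, LRTI) ignores the time of first dose, so a post-dose Day 1 value can stand as baseline.

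*SAP*

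**What the plan says.** SAP 3.5 sets one rule for three kinds of data (labs, vital signs, LRTI status): "the baseline window will be Day -2 to Day 1, without any consideration to exact time of assessment". Appendix 2.1 repeats this: "Baseline window will be Day -2 to 1 without any consideration to the time factor". Viral load is the only "exception to time is viral load, where baseline is within 1 hour post start of dosing", and SAP 6.6.1 restates that limit: "Only post-dose results that are within 1 hour post start of dosing will be treated as Baseline data".

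Appendix 2.1 then gives selection rules:

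- When screening and Day 1 records fall on one calendar day, the Day 1 record is used.
- Across different days, the reading nearer the target day is used.
- For labs and viral load on one day: "If different times on the same day, select the later one".
- Vital signs taken on one day within 10 minutes of each other are averaged.

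On timing, the protocol's Schedule of Activities (1.3) notes: "It is preferable for screening and randomization to occur on the same day". Randomization and the start of treatment share a day, and Protocol 6.1.1 places the first dose on Day 1, preferably at the visit.

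**The concern.** A baseline should describe the participant before treatment. If the first dose falls inside the baseline window and clock time is ignored, the date alone cannot separate untreated from treated records. The lab rule goes further: given a pre-dose and a post-dose sample on Day 1, it selects the post-dose one.

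For labs and vital signs, what is at stake is whether a safety value is judged against an untreated reference. For LRTI it is who belongs to which endpoint set, because the progression, development and resolution summaries are defined by status at randomization (SAP 6.2.1.1.2 to 6.2.1.1.4).

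**Working it through.** The plan gives no figure to reproduce. The check applies the Appendix 2.1 rules to the Day -1 and Day 1 records that the protocol allows.

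1. **Labs, scheduled sample only.** The Schedule of Activities requires Day 1 hematology and chemistry before first dose, and the next scheduled draw is Day 5. The baseline is correct.
2. **Labs, a second sample on Day 1.** Protocol 8.3.4 allows unscheduled labs at any time. With a pre-dose and a post-dose sample at different times on Day 1, the later-value rule makes the post-dose sample the baseline, although a valid pre-dose value exists. If instead the single scheduled sample is drawn late, it stands as baseline and nothing marks it.
3. **Vital signs, screening on Day -1 and visit on Day 1.** The Schedule of Activities does not say that Day 1 vital signs come before the dose. If they are taken after it, the Day 1 reading displaces the pre-dose screening reading, assuming that the baseline target day is Day 1 (the window table is not in the text available). Protocol 8.3.2.1 gives partial protection: blood pressure and pulse precede the laboratory blood draw, so at a compliant visit they also precede the dose. Temperature, respiratory rate and oxygen saturation have no such ordering.
4. **Vital signs, two Day 1 readings more than 10 minutes apart.** Within one nominal visit no rule chooses between them.
5. **Viral load.** A record more than 1 hour after the start of dosing cannot be baseline. The SAP therefore saw the issue for this measure and set a limit that the others lack.
6. **LRTI, wholly new.** Protocol Table 3 requires the qualifying signs or symptoms to last at least 24 hours. A Day 1 record made after a Day 1 dose is less than 24 hours after that dose, so any LRTI it shows began before treatment. At most, the 24 hours are completed after dosing.
7. **LRTI, non-severe to severe.** Protocol Table 4 gives its severity criteria no separate duration. A change recorded after dosing on Day 1 would be read as severe LRTI at baseline. The participant then leaves the progression set instead of counting as a progression, and the improvement endpoint becomes easier to meet, since moving from severe to non-severe now counts (SAP 3.2.1.2). The development and resolution sets do not change.

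For case 7, with *x* progressions among *n* participants in an arm, the proportion moves from *x*/*n* to (*x* − 1)/(*n* − 1). The drop is (*n* − *x*)/[*n*(*n* − 1)], which is 1/*n* when *x* = 1 and smaller for larger *x*. The documents do not give *n*, so no percentage-point figure can be stated.

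The SAP also treats first dose as the dividing line elsewhere in these endpoints: under SAP 6.2.1.1.2 and 6.2.1.1.3, an RSV-related hospitalization counts as an event only once dosing has begun. Baseline LRTI status has no matching line.

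**The case against.** The case against is strong on frequency. Scheduled Day 1 labs are pre-dose by protocol, so the lab error needs an extra or mistimed sample. When screening and randomization share a day, which the protocol prefers, vital signs and LRTI status are collected once, so there is no scheduled pair to choose between. The physical examination must precede dosing. The later-value rule covers labs and viral load, not vital signs or LRTI. Preferring the Day 1 record to screening is normal practice and does not by itself pick a post-dose value. SAP version 2 tests no hypotheses, and the only change from baseline it specifies is for viral load, which already has a time limit. Some derivation detail sits in the Analysis and Reporting plan, which is not available here.

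All of this stands, and it limits how often the rule does harm. It does not make the rule right: in case 2 the text, followed exactly, discards a valid pre-dose value for a post-dose one.

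A reader might infer more: that an LRTI first appearing after the Day 1 dose is turned from an event into a baseline condition, moving participants between denominators and shifting proportions by several points. The documents do not support that. The 24-hour criterion largely rules out wholly new LRTI on Day 1, same-day LRTI is assessed once, and the SAP describes enrollment only as very small, with no arm sizes.

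**Conclusion.** The point holds as a defect in the stated rule for labs and vital signs, with a narrow extension to LRTI. It is a minor point. The error should be rare, the analysis is descriptive, and neither error rates nor power are affected. An effect on proportions arises only through the narrow LRTI case and cannot be sized without arm counts.

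The conclusion rests on three assumptions: that the baseline target day is Day 1, that unscheduled or repeat Day 1 samples enter the same windowing, and that the Analysis and Reporting plan adds no pre-dose restriction.

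**What to change.** Replace the time-blind rule in SAP 3.5 and Appendix 2.1 as follows:

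- **Labs and vital signs:** baseline is the last non-missing assessment at or before first dose, by recorded times. Within the baseline window, choose the later value only among pre-dose records. Where a time is missing, use the record that was planned as pre-dose.
- **LRTI:** the documents do not show that a clock time is recorded for this assessment, so do not rely on one. Use the nominal Day 1 (or screening) assessment made at or before randomization, and do not let an unscheduled post-dose Day 1 record replace it.
- **No pre-dose record:** flag participants whose only Day 1 record is post-dose, and state the fallback.

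The cost is a few lines of SAP text and some programming. Protocol 6.5 already provides the dosing side: "Study intervention compliance and dose administration dates and times will be recorded in the CRF". The lab and vital-sign selection rules already presuppose assessment times. The only downside is handling the flagged participants.

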## Appendix 2.2. Endpoint Derivations

See the Analysis and Reporting plan for further details.

## Appendix 2.3. Definition of Protocol Deviations That Relate to Statistical Analyses/Populations

Not applicable.

## Appendix 3. Data Set Descriptions

See the Analysis and Reporting plan for further details.

## Appendix 4. Statistical Methodology Details

Not applicable.

## Appendix 5. List of Abbreviations

Abbreviation	Term
AE	adverse event
APAC	Asia/Pacific
ARI	acute respiratory infection
BLOQ	below the limit of quantitation
BMI CCI	body mass index
CCI	
CaPS	CDISC and Pfizer Standards
CDISC	Clinical Data Interchange Standards Consortium
CRF	case report form
CSR	clinical study report
ED	emergency department
E-DMC	external data monitoring committee
FAS	full analysis set
F/U	follow-up

Abbreviation	Term		
IA	interim analysis		
ICU	intensive care unit		
LLOQ	lower limit of quantitation		
LOD	limit of detection		
LRTI	lower respiratory tract infection		
MedDRA	Medical Dictionary for Regulatory Activities		
mITT	modified intent-to-treat		
N/A or NA	not applicable		
ND	not done		
NP	nasopharyngeal		
NS	no sample		
nsLRTI	non-severe LRTI		
nsLRTI-RSV	RSV-related nsLRTI		
PCR	polymerase chain reaction		
PK	pharmacokinetic(s)		
PO	per oral		
PT	preferred term		
CCI			
RNA	ribonucleic acid		
RSV	respiratory syncytial virus		
RT-PCR	reverse transcriptase PCR		
SAE	serious adverse event		
SAP	statistical analysis plan		
SD	standard deviation		
sLRTI	severe LRTI		
SOC	system organ class		
TD	target detected		
TEAE	treatment-emergent adverse event		
TND	target not detected		
UK	United Kingdom		

Abbreviation	Term
ULOQ	upper limit of quantitation
US	United States
